2c(ii)H1. Image Acquisition: After a short scout imaging scan to survey head position and center the field of view (FOV), a high resolution 3D magnetization prepared rapid gradient echo (MPRAGE) scan will be performed and used for co-registration and normalization of the functional image volumes to a Montreal Neurological Institute (MNI) space, as well as for the structural analyses. This high-resolution anatomical volume will be comprised of 160 sagittal slices and have 1.0×1.0×1.2 mm voxel dimension, as optimized by the Alzheimer’s Disease Neuroimaging Initiative protocol. Immediately following will be a 2:37 minute long gradient recalled echo (GRE) field mapping scan used for post-processing field inhomogeneity correction algorithms available in SPM’s FieldMap extension. This dual echo (TE 4.97 ms; 7.43 ms) whole-brain (39 axial slices; FOV 220×220 mm; voxel dimension 2.5×2.5×3.5 mm) scan will be manually shimmed to ensure optimization of the signal, especially in the ventral areas of the brain.

Resting state connectivity scan: Functional connectivity and activation scans will be acquired using a T2*-weighted gradient echo echo-planar imaging (EPI) sequence TR/TE 2250/29 ms; with same slice locations and voxel dimension as in the GRE field mapping scan. The prospective motion correction algorithm (3D-PACE, Siemens) providing a dynamic, real-time adjustment for detected head motion will be enabled. An integrated parallel acquisition technique reduction factor of 2 will be implemented with a generalized autocalibrating partially parallel acquisition (GRAPPA) to improve spatial resolution, reduce geometric distortion and scan time. For resting state functional connectivity 145 image volumes will be acquired in 5:33 min and two connectivity scans completed to address within-subject variability. Functional connectivity image volumes will be acquired while subject is in the resting state with eyes open and fixated on a cross and asked to think nothing in particular.

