a) Resting state functional connectivity (LFBF correlation): The time series data pre-processing (physiologic noise reduction, slice-timing correction, realignment, de-trending and bandpass filtering to extract low frequency BOLD fluctuations) will be accomplished using the AFNI software⁸⁷. SPM's (Wellcome Department of Cognitive Neurology, London, United Kingdom) mutual information algorithm will be applied to co-register each subject's high-resolution MPRAGE anatomical image to the mean of all functional connectivity image volumes and segment it into its tissue components. Three mean time-series, calculated by averaging across all brain, white matter and cerebrospinal fluid voxels will be utilized to account for any remaining global effects from each voxel's time series⁸⁸. The measures of functional connectivity will be evaluated on the AFNI pre-processed native-space connectivity volumes. We will either extract correlations between the mean time series of seed regions such as the amygdala and mean time series of another region such as the ventral anterior cingulate or calculate these correlations for all other voxels in the brain and thus generate connectivity maps. The more detailed description of the Pearson correlation coefficient calculation between the averaged LFBF time series of a-priori defined ROIs and its transformation to T-statistic was provided earlier⁴¹. Based on ACC region of the Talairach Daemon⁸⁹, ventral ACC (vACC) is defined as the rostral ventral part of the ACC resembling rostral Brodmann Areas (BA) 24 and 32, the area that has recently been reported to be involved in corticoamygdalar connectivity and mood regulation^{90,91}. The amygdalar ROIs will be defined using MarsBar's Montreal Neurological Institute (MNI) anatomical library definition but 10 mm diameter spherical regions centered at location (-23, -5, -15) and (23, -5, -15) will also be evaluated as adopted from the Talairach Daemon dataset⁸⁹. The medial and lateral OFC ROIs will also be defined from the MarsBar MNI anatomical library. The connectivity map approach used in our preliminary data analyses provides not only a measure of the regional connectivity but also its spatial distribution and can be utilized to fine-tune the seed region location, shape and size. These connectivity maps will be normalized to a common space by applying segmentation-generated transformation matrix, interpolated to 2 mm per side isotropic voxels and smoothed by a 6 mm full-width half-maximum (FWHM) Gaussian kernel. The resulting connectivity maps will be entered into SPM's second-level models (full factorial or paired-T design) to visualize as well as quantitate between-group differences. It should be noted that seed regions will be defined in the MNI space but that native-space ROIs will be checked using SPM's check-registration feature by overlaying them onto each subject's high-resolution anatomical and functional connectivity volumes. This procedure will detect low signal regions and normalization problems. Beside the above ROI seed based hypothesis driven analysis we will also explore other potential methods to conduct pattern analysis using independent and principal components analysis^{74,92}.

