Adjusting for covariates: These include behavioral rating such as, attentional variables such as response time, and accuracy of response, and changes in physiological ratings; demographic variables such as age, gender, and ethnicity; scores on behavioral measures such as anxiety; treatment with concomitant medications such as atypical neuroleptics during the study; treatment history, substance abuse, and trauma history; and structural variables such as whole brain and ROI volumes. We will first identify the covariates with highly correlated with the outcome measures. Next, from this pool of highly correlated covariates to guard against multicollinearity and to conserve for degrees of freedom to ensure that we have sufficient power. To control for potential confounding effects from these covariates and not over-fit in any of our models, we will use the forward stepwise regression model building approach - so that only one covariate will be included at a time in the model - which allows us to screen out covariates that are not related to our outcome measures by using an elevated p-value ($p=0.1$) and reserve statistical power to a limited number of variables that are shown to be associated with outcome measures in our data⁹⁸.

2c(ii)lb. Sample size and power consideration: Preliminary data obtained from BDD and UD subjects were compared with healthy subjects to obtain estimates of sample size at significance level set at 0.05. Proc Power of SAS software is used to estimate the sample size.

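### Residual head motion is neither a named nuisance regressor nor a listed covariate, so a group difference in it could bias the connectivity contrasts by an unknown amount

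*Combined protocol and SAP*

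**What the plan says.** Motion is addressed at two points in the resting-state pipeline. At acquisition (2c(ii)H1), "The prospective motion correction algorithm (3D-PACE, Siemens) providing a dynamic, real-time adjustment for detected head motion will be enabled". In preprocessing (2c(ii)H2 a), realignment is one item in "physiologic noise reduction, slice-timing correction, realignment, de-trending and bandpass filtering to extract low frequency BOLD fluctuations".

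The nuisance time series are then named: "Three mean time-series, calculated by averaging across all brain, white matter and cerebrospinal fluid voxels will be utilized" to account for remaining global effects. The registration check that follows looks for something other than movement: "This procedure will detect low signal regions and normalization problems". No regression on motion parameters, volume censoring, per-subject motion summary or motion exclusion limit is given.

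The covariate paragraph of 2c(ii)la covers "attentional variables such as response time, and accuracy of response, and changes in physiological ratings", then demographics, anxiety, concomitant medication, treatment, substance and trauma history, and "structural variables such as whole brain and ROI volumes". Head motion is not named. Covariates enter by forward stepwise selection, intended to "screen out covariates that are not related to our outcome measures by using an elevated p-value" of 0.1.

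The resulting connectivity values are compared between diagnostic groups by one-way ANOVA in Aims 1 and 2. In Aim 1 a logistic classifier is then built and assessed by leave-one-out cross-validation.

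**The concern.** The connectivity outcome is a correlation between two regional time series. 3D-PACE and realignment correct head position. They do not model the signal change that movement leaves in the series, and what survives can shift the correlation.

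In a randomised comparison, residual motion would be balanced in expectation. Here the groups are diagnostic. Section E1a matches on age, gender and ethnicity, and matches BDD with UD on depression severity, but not on movement. If one group moved more, the difference could create a connectivity contrast or hide a real one. Blinded image analysis would not remove it. Leave-one-out validation would not expose it either, because the same confounder is present in every fold.

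**Working it through.** **Text check.** The plan states no figure for motion, so there is nothing to reproduce. Going through the pipeline in order:

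| Stage | Section | Motion handling named |
|---|---|---|
| Acquisition | 2c(ii)H1 | 3D-PACE |
| Preprocessing | 2c(ii)H2 a | Realignment |
| Nuisance series | 2c(ii)H2 a | Whole brain, white matter, CSF; no motion parameters |
| Image check | 2c(ii)H2 a | Low signal and normalization only |
| Group covariates | 2c(ii)la | None |

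**Illustration of possible bias (assumed inputs).** Let m be the group difference in residual motion in SD units and r the correlation of motion with connectivity. With no true difference, the spurious standardised difference is d = m × r. The values of m and r are assumptions, because the documents give none.

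- Low case: m = 0.3, r = 0.2, so d = 0.06.
- High case: m = 0.5, r = 0.4, so d = 0.20.
- If m = 0 or r = 0, then d = 0.

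Group sizes are 40 BDD and 120 UD, and alpha is 0.05 (both from 2c(ii)lb). A two-sided test is assumed. The noncentrality is d / √(1/40 + 1/120) = d / 0.1826, which gives 0.329 for d = 0.06 and 1.095 for d = 0.20. The rejection probability comes from the noncentral t distribution with 158 degrees of freedom.

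| Spurious d | 40 vs 120, alpha 5% | 32 vs 96 (20% attrition), alpha 5% | 40 vs 120, alpha 1.7% |
|---|---|---|---|
| 0 | 5.0% | 5.0% | 1.7% |
| 0.06 | 6.2% | 6.0% | 2.3% |
| 0.20 | 19.3% | 16.3% | 9.6% |

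The last column reflects the Bonferroni adjustment specified for Aim 1. The plan does not give the number of tests, so three are assumed (0.05 / 3 = 1.7%).

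**Would stepwise entry be enough?** Suppose motion were offered to the stepwise procedure, with a true correlation of 0.2 with the outcome in 160 subjects. On a univariate screen, Fisher's z is 0.2027 × √157 = 2.54, against a two-sided critical value of 1.645 at p = 0.1. The chance of missing it is Φ(1.645 − 2.54) = Φ(−0.895), or about 18%.

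**Within-run cost of motion regressors.** A run lasts 145 × 2.25 s = 326 s (2c(ii)H1). Taking the 0.08 Hz limit from 2a(iii) as the upper cut-off, there are at most about 2 × 326 × 0.08 = 52 temporal degrees of freedom. Six realignment regressors use about 6 / 52 = 12% of them.

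**The case against.** The strongest reply is that motion is not ignored. 3D-PACE and realignment act on it directly, and removing the three tissue signals takes out part of any motion-related signal. Physiologic noise reduction is a separate step whose content is not spelled out, and two connectivity runs are acquired. This stands, and it is why the point concerns residual motion only.

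The covariate list is introduced as illustrative, so motion is unnamed rather than ruled out. That also stands, but adding it to a stepwise pool would not secure adjustment. The plan also refers to earlier publications for the correlation calculation and for the general form of the Aim 1 analyses. Those cannot be checked here, so the finding is that motion regression is not stated in this plan. It is not that it will not be done.

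BDD and UD subjects are both currently depressed, have the same severity limits, must be free of recent psychotropics, and are to be matched on depression severity. Nothing in the documents shows that they differ in movement. A reader might infer from the illustration that the BDD vs UD test has a true error rate of 6% to 19%. The documents do not support this: the inputs are assumed, and the figure is for a test without the planned Bonferroni adjustment.

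A reader might also set 0.06 to 0.20 SD beside the 0.15 effect size in 2c(ii)lb and conclude that motion alone could mimic the effect the study is powered for. That comparison should not be made. The unit of 0.15 is not stated. If it were SD, power at 40 vs 120 would be about 13%, not the stated 80% or more.

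**Conclusion.** The point holds as a gap in confounder control. As written, the pipeline reduces motion effects but leaves whatever remains unmodelled within subjects and unadjusted between groups, in a comparison that randomisation does not protect. The Aim 1 and 2 connectivity contrasts and the classifier are exposed.

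The size and direction of any bias are unknown. The illustrative rise from 5% to about 6% to 19% rests on an assumed motion difference of 0.3 to 0.5 SD and an assumed motion-connectivity correlation of 0.2 to 0.4. With three Bonferroni tests, also assumed, the per-test rate goes from 1.7% to between 2.3% and 9.6%. With equal motion in the groups there is no inflation. The point supports a recommended improvement to the analysis plan, not a claim that the results will be biased.

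**What to change.** In 2c(ii)H2 a), add the realignment parameters to the nuisance regression alongside the three tissue series. In 2c(ii)la, enter each subject's mean frame-to-frame displacement as a forced covariate, outside the stepwise procedure, in every Aim 1 and 2 connectivity model. Report displacement by group and give the result without motion adjustment as a sensitivity analysis.

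With 3D-PACE on, post-hoc realignment parameters mainly reflect the movement that PACE did not correct. The plan should therefore also use the motion estimates logged by PACE where they are available.

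The cost is revised wording, one degree of freedom at group level, and about six temporal degrees of freedom in each 145-volume run (roughly 12% of those available under the 0.08 Hz assumption). No extra scans or visits are needed, and realignment already produces the parameters.

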Specific Aim 1: Differentiation between BDD and UD: We will conduct a one way ANOVA with the connectivity and activation measures as dependent variables to look at differences between groups (BDD and UD). The analyses will be similar to those in our previous studies^{41, 42}. The normality assumptions will be examined using the Kolmogorov-Smirnov test. Box-Cox type transformation methods will be employed if the normality assumption is violated for the outcome variable. To adjust for multiple comparisons accounting for multiple brain ROIs and ad-hoc comparisons conducted within an ANOVA model, Bonferroni adjustment will be used to control overall type I error rates (over-all significance level will be set to 0.05). A post ANOVA logistic regression based classification model will be constructed to build a classifier between BDD and UD. Specificity and sensitivity will be examined using receiver operating characteristics (ROC) curves. We will use leave-one out cross validation method to assess predictive performance of our classification model⁹⁶.

Specific Aim 2: Differentiation between BDD, HRUD, LRUD and healthy control: We will use corticoamygdalar connectivity, amygdalar-LOFC connectivity and ACC Activation in Emotion to perform one-way ANOVA among all four groups. Prior to the analysis, each of these variables will be transformed (using the Box-Cox transformation) so that they will made as close to Gaussian as possible. The normality assumptions will be examined using the Kolmogorov-Smirnov test. Specificity and sensitivity will be examined as in Aim 1.

Specific Aim 3: Identification of imaging measures significantly affecting the rate of conversion from UD to BD: The conversion of UD subjects into BDD is defined as the time to event phenomenon and will be modeled using Cox-proportional hazard model given by,

$$\log(h(t)) = h_0(t) + \beta_1 X_1 + \beta_2 X_2 + \dots + \beta_p X_p$$

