Specific Aim 1: We used our pilot data for Left LOFC-amygdala connectivity measure. This data yielded an effect size of 0.27 for difference between BDD and UD group. 40 samples in the BDD and 120 samples in UD group will give us more than 80% power to detect an effect size as low as 0.15 for the difference in Left LOFC-amygdala connectivity between two groups. Probability of type 1 error (alpha) was set always at 0.05. For ACC-left amygdalar connectivity measure, the effect size is 0.482. With previous mentioned sample size for each group we will have 90% power to detect an effect size as low as 0.3. Similar conclusion can be made for ACC activation in NoGo-Go task for which the data yielded an effect size of 0.726 for difference between BDD and UD group. Our proposed sample size is enough to detect the difference of effects with a power close to 90% at a significance level of 0.05. Even with 20% attrition rate (i.e. 32 BDD and 96 MDD) this sample size is large enough to ensure 80% power at alpha 0.05.

Specific Aim 2: For comparisons among BDD, HRUD, LRUD and healthy subjects all three connectivity and activation measures produce power more than 80% for 40 subject per group to detect a significant difference. In the present case with 40 BDD, 60HRUD and 60 LRUD samples the power calculation is little involved, nevertheless increased sample size ensures more than 80% power at alpha= 0.05. To compare HRUD vs. LRUD left LOFC-amygdala connectivity measure yields an effect size of -0.254. For 60 subjects/group this produces 88% power at alpha 0.05.

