3. HUMAN SUBJECTS

E1a. Human Subjects Characteristics:

The human subjects age range 16 - 30 yrs (inclusive) involved in this study will be - 40 BDD, 60 HRUD, 60 LRUD and 40 healthy control subjects matched as a group for age, gender and ethnicity who will be studied at baseline. BDD and UD subjects will be matched for depression severity at the time of the scan. However, it is likely that, by definition the BDD and UD subjects will be different in terms of other illness characteristics such as duration of illness, number of episodes, and history of alcohol and substance abuse. We will treat those illness variables as covariates in our statistical analysis (as described in section 2c(ii)1a above) to take into account the potential confounding effects of some of these variables.

Inclusion criteria for BDD patients:

1. Ages 15 - 30 years (inclusive) and able to give voluntary informed consent (consent will be taken from both parents and child for children under the age of 18)
2. Satisfy criteria for Diagnostic and Statistical Manual 4th edition (DSM-IV-TR) for Bipolar I or II disorder
3. Satisfy criteria for DSM-IV depressive episode-current
4. 17-item Hamilton Depression Rating Scale > 15 but < 25;
5. Young Mania Rating Scale score < 10
6. Satisfy criteria to undergo an MRI scan based on MRI screening questionnaire.
7. Able to be managed as outpatients during the study as ascertained by the following –
 - i. Clinical Global Severity Scale < 5 i.e. moderately ill;
 - ii. No significant suicidal or homicidal ideation or grossly disabled.

Inclusion criteria for All UD patients:

1. Ages 15 - 30 years and able to give voluntary informed consent (consent will be taken from both parents and child for children under the age of 18).
2. Satisfy criteria for DSM-IV-TR Major Depressive Episode using a Structured Interview
3. Never met criteria for mania or hypomania
4. 17-item Hamilton Depression Rating Scale score (HDRS) > 15 and < 25.
5. Young Mania Rating Scale (YMRS) score < 10
6. Satisfy safety criteria to undergo an MRI scan
7. Able to be managed as outpatients during the study as ascertained by the following –
 - i. Clinical Global Severity Scale < 5 i.e. moderately ill;
 - ii. No significant suicidal or homicidal ideation or grossly disabled

Additional Inclusion criteria for High Risk UD (HRUD) patients beside the inclusion criteria for UD:

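### Aim 1 compares 40 BDD with 120 UD subjects by an unqualified one-way ANOVA with no provision for unequal variances, and the map analysis allows a paired design between groups that have no pairs

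*Combined protocol and SAP*

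**What the plan says.** Section 2c(ii)la, Specific Aim 1: "We will conduct a one way ANOVA with the connectivity and activation measures as dependent variables", with BDD and UD as the groups. On assumptions it says "The normality assumptions will be examined using the Kolmogorov-Smirnov test". A Box-Cox transformation follows in Aim 1 only if normality fails. On error control it says "Bonferroni adjustment will be used to control overall type I error rates", and "over-all significance level will be set to 0.05". The number of tests is not given.

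The same section, Specific Aim 2, runs a one-way ANOVA over BDD, HRUD, LRUD and healthy controls (40/60/60/40). Here every variable is Box-Cox transformed beforehand, and normality is again the only assumption examined.

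Section 2c(ii)lb sizes Aim 1 on "40 samples in the BDD and 120 samples in UD group". It then allows for losses: "Even with 20% attrition rate (i.e. 32 BDD and 96 MDD". That is still 1:3.

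Section 2c(ii)H2 a) sends the connectivity maps to second-level models described as "full factorial or paired-T design) to visualize as well as quantitate between-group differences". Section E1a says the subjects are "matched as a group for age, gender and ethnicity". Section 2c(ii)H1 has each subject complete two resting connectivity scans.

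Neither aim has a variance check, an unequal-variance test or a robust standard error. Homogeneity is mentioned once, as an assumption in the Aim 3 sample-size text.

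**The concern.** The classical F test tolerates unequal variances reasonably well when group sizes are equal, but not at 1:3. The pooled variance is then dominated by the larger group. If the small BDD group is the more variable, the standard error of the difference is understated and false positives rise. If it is the less variable, the standard error is overstated and power is lost. A normality test detects neither case.

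At stake is the claim that the main BDD-versus-UD comparison controls overall type I error at 0.05. Bonferroni does not repair this, because it divides a per-test level that may itself be wrong. The plan does prespecify a check and a remedy for proportional hazards in Aim 3, so a similar provision here would fit its own practice.

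The paired model is a separate problem and needs no assumption about SDs. A paired test of BDD against UD requires a rule linking each BDD subject to one UD subject, and the plan has none.

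**Working it through.** **Inputs.** From the documents: n = 40 and 120 (32 and 96 after attrition); overall alpha 0.05; Aim 2 sizes 40/60/60/40. Assumed, because the documents give no SDs: the ratio r = SD(BDD)/SD(UD), with the UD SD set to 1 and normal data.

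**Formula.** For 40 vs 120:
- variance of the difference that the pooled test uses, on average: P = [(39r² + 119)/158] × (1/40 + 1/120)
- true variance of the difference: T = r²/40 + 1/120
- approximate type I error: 2 × [1 − Φ(1.975 × √(P/T))], where 1.975 is the two-sided 5% point of t on 158 df.

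**The plan's own figure.** At r = 1, P = T = 0.0333. Simulation gives 5.0%, the stated alpha. The normal approximation gives 4.8%.

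**r = 1.5.** P = (87.75 + 119)/158 × 0.03333 = 0.0436. T = 0.05625 + 0.00833 = 0.0646. √(P/T) = 0.822, and 1.975 × 0.822 = 1.623, so the error is about 10.5%. Simulation gives 10.7%.

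**r = 0.67.** P = (17.33 + 119)/158 × 0.03333 = 0.0288. T = 0.01111 + 0.00833 = 0.0194. √(P/T) = 1.216, and 1.975 × 1.216 = 2.402, so the error is about 1.6%. Simulation gives 1.7%.

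**Type I error over the range** (200,000 simulated data sets per setting):

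| SD ratio BDD/UD | Pooled, 40 vs 120 | Welch, 40 vs 120 |
|---|---|---|
| 0.67 | 1.7% | 5.0% |
| 0.8 | 2.9% | 5.0% |
| 1 | 5.0% | 5.0% |
| 1.25 | 7.9% | 5.0% |
| 1.5 | 10.7% | 5.0% |
| 2 | 15.2% | 5.0% |

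With 32 vs 96 the pooled figures are almost the same (10.7% at 1.5, 15.2% at 2).

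**Under Bonferroni.** The plan gives no number of tests. Assuming three independent ones (0.05/3 = 0.0167 each), the pooled test at r = 1.5 rejects 4.9% per test, about three times nominal. The family-wise error is then 1 − (1 − 0.0488)³, about 14%.

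**Power.** This reads the plan's 0.482 as a difference in UD SDs, although the plan does not say what kind of effect size it is. At r = 0.8, power is 81% pooled and 86% Welch. At r = 1 it is 74.6% pooled and 73.9% Welch.

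**Aim 2.** If only BDD has a different SD, the classical four-group F test rejects 4.5% at ratio 0.67, 6.8% at 1.5 and 8.9% at 2. Welch's F gives 4.9% to 5.1%. HRUD vs LRUD tested alone (60 vs 60) stays at 5.0% to 5.1% even when their SDs differ by a factor of 1.5 or 2. If the follow-up contrasts instead use the four-group pooled error, then at BDD ratio 1.5, BDD vs LRUD rejects about 9.7% and HRUD vs LRUD about 3%, so they are distorted in opposite directions.

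**Paired model.** Section 2c(ii)H2 a) attaches it to differences between groups. Section E1a matches groups, not individuals, and 40 cannot be paired one-to-one with 120. The only natural pairs in the design are each subject's two resting scans. Those are within subject, and the text does not assign the paired model to them.

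**The case against.** The strongest objection is that the harm is conditional on something nobody can see. The documents give no group SDs, so neither the size nor the direction of any inequality is known. UD pools high-risk and low-risk patients and could well be the more variable group, in which case the test is conservative. This stands. A reader might infer from the table that the trial's type I error is 11%, or at most 11%. The documents support neither reading: 11% belongs to an SD ratio of about 1.5 with BDD more variable, a ratio of 2 gives 15%, and reversing the direction gives under 2%.

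Nor do the Aim 1 figures carry over to every group test. Aim 2 is not 40 vs 120, and its omnibus inflation is milder. Its routine Box-Cox step may also even out variances to some degree, although it is aimed at normality. In Aim 1 that step is triggered only by non-normality.

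The documents never use the term pooled variance. It is the ordinary meaning of a one-way ANOVA named without qualification. The section also says the analyses resemble earlier studies, which cannot be consulted here.

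On the paired model, one might conclude that the design contains no pairs at all, or that BDD subjects will in fact be paired with UD subjects and most of the UD group discarded. Neither follows. Within-subject pairs exist, and the same bracket offers a full factorial model, which suits independent groups. What stands is narrower: the wording permits a paired model for between-group contrasts, where it cannot be valid.

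**Conclusion.** The concern holds in conditional form. For Aim 1 the claimed 0.05 error rate rests on equal variances, which the plan neither states for this test nor checks, in a 1:3 comparison where that assumption matters. Over assumed BDD/UD SD ratios from 0.67 to 2, the pooled test's type I error runs from about 2% to about 15%, while Welch's stays near 5%. For Aim 2 the omnibus error is about 7% to 9% if BDD alone is 1.5 to 2 times as variable. These figures assume normal data and an ANOVA of the pooled form. They show how exposed the test is and do not predict its error rate in this trial. That between-group pairs do not exist follows from the documents alone. Both points should be corrected, and neither calls for a change in design or sample size.

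**What to change.** In section 2c(ii)la, prespecify Welch's ANOVA for the Aim 1 and Aim 2 ROI tests and Welch contrasts for the pairwise comparisons, with Bonferroni applied to those p-values. Where covariates are added, use heteroscedasticity-consistent (HC3) standard errors. Make this the default rather than conditional on a preliminary variance test.

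In section 2c(ii)H2 a), remove the paired-T option for between-group contrasts and name the independent-groups model with unequal variances. If a paired model was meant for the two resting scans within a subject, say so there.

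The cost is SAP wording, plus under 1 point of power if variances turn out equal (74.6% to 73.9% at a standardised difference of 0.482; 97.7% to 97.5% at 0.726).

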
b) Regional Activation Analysis: Functional image volumes in NoGo-Go task will be processed using SPM standard individual first level modeling. Group effects will be obtained using a second level analysis within SPM. Furthermore, a priori defined ROIs will be used to extract mean activation effects for between-group statistical analyses and to collect ROI percent signal change in response to various emotional and non-emotional NoGo-Go conditions. The primary contrast for analysis would be Happy NoGo-Go and Sad NoGo-Go compared to letter NoGo-Go to measure regional brain activation specifically for response inhibition to emotional stimuli. Corrections for multiple comparison/multiple hypothesis will be performed using the false discovery rates⁹³.

c) Volumetric Analysis: While structural analysis is not part of the aims of this proposal we will conduct structural analysis on the high-resolution anatomical scan to explore correlations with functional measures of activation and connectivity. A semiautomated cortical reconstruction and volumetric segmentation will be

performed as previously reported by the investigators⁹⁴ with the Freesurfer image analysis suite⁹⁵. This process generates individual regional measures for cortical and subcortical anatomic structures. We will register individual maps to a standardized atlas and will apply a GLM approach to compare morphometric features across individual subjects and between study groups.

2c(ii)la. Statistical Analysis:

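### Holm's step-down could replace single-step Bonferroni for the Aim 1 ROI and ad-hoc comparisons at the same 5% familywise error, and the false discovery rate rule for activation needs its scope stated

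*Combined protocol and SAP*

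**What the plan says.** Section 2c(ii)la (Statistical Analysis), Specific Aim 1, plans a "one way ANOVA with the connectivity and activation measures as dependent variables" to compare BDD with UD. The multiplicity rule has a stated scope, "To adjust for multiple comparisons accounting for multiple brain ROIs and ad-hoc comparisons conducted within an ANOVA model", and a stated method and level: "Bonferroni adjustment will be used to control overall type I error rates (over-all significance level will be set to 0.05"). The number of tests in the family is not given, the Aim 1 text does not list the ROI tests, and no step-down procedure is mentioned.

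Section 2c(ii)H2, part b (Regional Activation Analysis), describes second-level modelling in SPM. It adds that "a priori defined ROIs will be used to extract mean activation effects for between-group statistical analyses". It then names the contrasts and closes with: "Corrections for multiple comparison/multiple hypothesis will be performed using the false discovery rates". The reference attached to that sentence (no. 93) is, by its title, about thresholding statistical maps.

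Section 2c(ii)lb (Sample size and power consideration) makes no allowance for multiplicity: "Probability of type 1 error (alpha) was set always at 0.05".

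**The concern.** There are two separate issues.

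**Efficiency.** Single-step Bonferroni tests every measure at 0.05/m, however many of the others have already been rejected. Holm tests the smallest p-value at 0.05/m, the next at 0.05/(m−1), and so on, stopping at the first failure. It rejects everything that Bonferroni rejects, sometimes more, and needs no assumption about how the measures are correlated. Hypothesis 1 predicts real differences on LOFC-amygdala connectivity, vACC-amygdala connectivity and dACC activation. Holm helps most when most tests in the family are real effects. The smaller group has only 40 subjects, or 32 after the 20% attrition that the plan allows for.

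**Clarity.** Activation measures are outcomes of the Aim 1 ANOVA, so the Bonferroni rule covers them. The a priori activation ROI tests also sit in the paragraph that ends with the false discovery rate. The false discovery rate does not control the familywise error that the Aim 1 text claims. On the wording, dACC activation could be significant under one rule and not under the other, and no sentence says which applies.

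**Working it through.** **The plan's own figures.** For 40 vs 120 at alpha 0.05, section 2c(ii)lb states more than 80% power for an effect size of 0.15, 90% for 0.3 and close to 90% for 0.726. A two-sided two-sample t-test with these values read as Cohen's d gives 12.9%, 37.2% and 97.7%. Read as Cohen's f they give 47.1%, 96.5% and about 100%. Neither reading reproduces the statements, and the plan states no power after Bonferroni. The comparison below therefore uses the plan's pilot effects, with the scale as an assumption.

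**Inputs from the documents.** Group sizes are 40 and 120. Familywise alpha is 0.05. Pilot effects are 0.27 (left LOFC-amygdala), 0.482 (ACC-left amygdala) and 0.726 (ACC activation, NoGo-Go), taken here to stand for the three Hypothesis 1 measures.

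**Assumptions.** Family size m = 3, effects on the d scale, two-sided tests, correlation 0.3 between the test statistics, and all three effects real.

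**Bonferroni by formula.** The noncentrality is d × √(40 × 120 / 160) = d × √30 = 5.477d, which is 1.479, 2.640 and 3.976. The two-sided critical value at 0.05/3 is 2.394. Power is close to Φ(5.477d − 2.394): 18%, 60% and 94%.

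**Holm by simulation**, using correlated normal test statistics with those noncentralities:

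| Measure | Bonferroni | Holm |
|---|---|---|
| LOFC-amygdala (0.27) | 18% | 29% |
| ACC-amygdala (0.482) | 60% | 67% |
| ACC activation (0.726) | 94% | 95% |
| All three significant | 14% | 26% |

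The chance of at least one rejection is the same under both methods, because both test the smallest p-value at 0.05/m.

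**Error rate.** With three true nulls, the familywise error of Holm in simulation is 4.8% to 4.9%. With one null and two real effects (0.482 and 0.726), the null is rejected 4.0% of the time under Holm and 1.6% under Bonferroni. Both are within 5%.

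**Sensitivity of the gain.**
- Correlation: with three real effects at 40 vs 120, the largest gain on any measure is 9.9 points at correlation 0, 10.8 at 0.3 and 11.5 at 0.5.
- Attrition to 32 vs 96, correlation 0.3: 14% to 23%, 49% to 56%, and 88% to 89%.
- One of the three measures null: the largest gain on a real effect is about 4 to 6 points, depending on the correlation and on which measure is null. Two null: 0.1 point.
- Three null tests added to the three pilot effects (m = 6): gains of 2.5, 2.7 and 0.4 points.
- Six null tests added (m = 9): gains of 1.1, 1.6 and 0.3 points.

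**The two rules side by side.** The Aim 1 text applies Bonferroni to connectivity and activation outcomes across ROIs. The activation paragraph applies the false discovery rate to multiple comparisons and multiple hypotheses, after a sentence on between-group tests of a priori ROIs. Nothing in that paragraph confines the rule to maps. Only the title of the cited reference points that way.

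**The case against.** The strongest reply is that nothing here is wrong. Bonferroni at an overall 0.05 is valid, contradicts no aim and is simple to report. That stands, so this is a point about efficiency and clarity.

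The second reply is that the gain is a best case. The Bonferroni family is not counted, and it could be much larger than three. Section 2c(ii)H2 mentions left and right amygdala, two amygdala definitions, and medial as well as lateral OFC. Hypothesis 1 adds comparisons with healthy controls, and the rule itself takes in ad-hoc comparisons. If several of these are null, little of the gain remains. Even in the favourable case, the largest gain goes to the weakest measure, which stays at about 29% power, and dACC activation gains about 1 point. This stands too, and it limits the size of the claim.

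The third reply is that the two rules need not conflict. The false discovery rate sentence is in the image analysis section and cites a source on statistical maps, while Bonferroni is in the statistical analysis section and concerns ROIs. A reader might infer that the plan sets two contradictory rules for dACC activation. The documents do not go that far: maps under one rule and ROIs under the other is a natural reading. The wording still reaches the a priori ROI tests, so the ambiguity is real but mild.

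**Conclusion.** Replacing Bonferroni by Holm is a free improvement. It keeps the 5% familywise error under any dependence and never loses a rejection. Under the assumptions listed (three measures, d scale, correlation 0.3, all effects real), it adds about 11, 7 and 1 points of power, and raises the chance that all three measures are significant from 14% to 26%. With three or more null tests in the family, the gain is about 3 points or less per measure.

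A reader might infer a gain of about 10 points on each measure. The documents do not support that. The family size, the effect-size scale and the correlation are not stated, and a gain of that size appears only on the weakest measure with every effect real. Nor does Holm rescue the stated Aim 1 power, which is a separate and larger problem.

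The overlap between the two multiplicity rules is an ambiguity of wording that should be closed before the group comparisons are run.

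**What to change.** In section 2c(ii)la, Specific Aim 1, first list the family: LOFC-amygdala connectivity, vACC-amygdala connectivity and dACC activation, plus every other ROI and ad-hoc comparison that the present rule covers. Then replace Bonferroni by Holm across that one list at an overall 0.05. The ad-hoc comparisons must stay inside the family. If Holm were applied to the three measures alone and the rest left out, the overall 5% claim would no longer hold.

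In section 2c(ii)H2, part b, state that the false discovery rate applies to voxelwise maps only, and that the a priori ROI tests follow the Aim 1 rule.

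The cost is a listed family and two edited sentences. No subjects, data or familywise error are added. The one small downside is that simultaneous confidence intervals matched to Holm are less simple. The plan does not call for any, and unadjusted or Bonferroni intervals, labelled as such, can be reported alongside.
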